2. SYNOPSIS

Name of Sponsor/Company: Reata Pharmaceuticals	
Name of Investigational Product: RTA 408 Lotion	
Name of Active Ingredient: RTA 408	
Title of Study: A Randomized, Double-blind, Vehicle-controlled, Parallel-group Phase 2 Study of the Efficacy, Safety, Pharmacokinetics and Pharmacodynamics of RTA 408 Lotion in the Treatment of Patients at Risk for Radiation Dermatitis	
Study center(s): Up to 35 study centers in the US	
Studied period (years): < 1 Estimated date first patient enrolled: June 2014 Estimated date last patient completed: May 2015	Phase of development: 2
Objectives:	
Primary: 
 • To determine the time-averaged effect on radiation dermatitis grade measured with Common Terminology Criteria for Adverse Events (CTCAE, Version 4.03) following 3D conformal radiation therapy to the breast and concomitant administration of RTA 408 Lotion (0.5% and 3%) compared to administration of vehicle • To evaluate the safety of RTA 408 Lotion 	
Secondary: 
 • To determine the mean maximum radiation dermatitis grade measured with CTCAE of RTA 408 Lotion (0.5% and 3%) compared to administration of vehicle • To determine the proportion of patients with treatment success, defined as post-baseline maximum dermatitis grade < 2 using the CTCAE criteria following administration of RTA 408 Lotion compared to administration of vehicle • To determine the mean duration of grade ≥ 2 radiation dermatitis using the CTCAE criteria following administration of RTA 408 Lotion compared to administration of vehicle • To determine the extent of systemic exposure to RTA 408 following administration of RTA 408 Lotion following radiation therapy • To evaluate patient-reported outcomes (Skindex-16) 	
Methodology: This double-blind, randomized, vehicle-controlled, parallel-group study will assess the safety, tolerability, and efficacy of RTA 408 Lotion (0.5% or 3%) versus vehicle in the treatment of patients at risk for radiation dermatitis. Eligible patients will be randomized using a 1:1:1 assignment ratio to receive RTA 408 Lotion 0.5%, RTA 408 Lotion 3%, or vehicle and will be stratified by smoking status (smoker or ex-smoker versus non-smoker) and breast cancer treatment prior to radiation therapy (full mastectomy versus partial mastectomy or lumpectomy). Study drug application will start	

approximately 1 week prior to scheduled initiation of radiation therapy with twice daily applications continuing throughout the duration of radiation therapy (i.e., 5-6 weeks) and two weeks following completion of radiation therapy, for an expected total of up to 9 weeks of study drug application. In cases where radiation treatment is delayed (e.g., delayed radiation treatment initiation or radiation treatment interruptions), the total study drug application period may be extended from the expected 8-9 weeks up to a maximum of 13 weeks. Study drug is to be applied twice daily. On days of morning radiation treatments, the patient will apply the study drug at the radiation treatment center immediately after the radiation therapy concludes and at night before bed. On days of afternoon radiation treatments, the patient will apply the study drug in the morning at least 4 hours before radiation treatment and at night before bed. Any residual lotion from a prior application should be removed prior to radiation treatment. Following randomization, patients will be assessed in person at weekly visits during administration of study drug. A follow-up visit will occur 4 weeks after the last application of study drug.

Number of patients (planned):

Approximately 177 patients will be enrolled in this study with 59 patients in each of the three groups

Diagnosis and main criteria for inclusion:

Key inclusion criteria:

1. Adult female patients (18 to 80 years of age, inclusive);
2. Patients diagnosed with ductal carcinoma *in situ* or non-inflammatory breast adenocarcinoma who have been referred for post-operative radiotherapy to one breast and have had no prior radiation treatment to that breast;
3. Patients planning to undergo 3D conformal radiation therapy to the whole breast (as part of breast-conservation therapy / lumpectomy) or chest wall (as part of post-mastectomy irradiation), with or without treatment of regional lymph nodes (i.e., axillary, supraclavicular, or internal mammary), using one of the following treatment schedules:
 - a. 45 – 50.4 Gy in 1.8 Gy per day, in addition to a mandatory 10-16 Gy boost
 - b. 46 – 50 Gy in 2 Gy per day, in addition to a mandatory 10-16 Gy boost;
4. Patients who received breast-conservation therapy / lumpectomy must be receiving $\geq 107\%$ of the total radiation dose (calculated from the total radiation dose including boost) to any portion of the breast, based on radiation inhomogeneity, **and/or** have a breast volume ≥ 1200 cc;
5. Female patients of childbearing potential who are willing to practice methods of birth control from screening through 1 month after applying the final dose of study drug;
6. Female patients of childbearing potential who are non-pregnant, non-lactating and have a negative pregnancy test result prior to enrollment in the study;
7. Patients willing and able to give written informed consent for study participation;
8. Patients willing and able to cooperate with all aspects of the protocol.
9. Patients for whom at least 14 days have elapsed since breast conservation surgery, mastectomy surgery and/or chemotherapy prior to randomization;
10. Have adequate hematologic and organ function at screening as follows:
 - Hematologic: Absolute neutrophil count $\geq 1.5 \times 10^3 / \mu\text{L}$, platelets $> 100 \times 10^9 / \text{L}$, hemoglobin $\geq 9 \text{ g/dL}$;
 - Hepatic: total bilirubin ≤ 2 times (X) upper limit of normal (ULN), ALT and AST $\leq 2X$ ULN;
 - Renal: serum creatinine $\leq 1.5 \text{ mg/dL}$

Key exclusion criteria:

1. Patients with TNM Classification T4 or Stage IV breast cancer;
2. Patients with prior radiation therapy to the breast treated in this study;
3. Patients with type V or VI skin according to the Fitzpatrick scale;
4. Patients with current bilateral breast cancer who are receiving radiation treatment in both breasts;
5. Patients receiving partial breast irradiation therapy;
6. Patients with uncontrolled diabetes (HbA1c > 11.0%, historical values within 6 months of screening are acceptable);
7. Patients with collagen vascular disease or vasculitis;
8. Patients with concurrent active malignancy other than adequately treated basal cell carcinoma of the skin or carcinoma *in situ* of the cervix;
9. Patients with active and not adequately treated bacterial, fungal, or viral skin infections, at the investigator's discretion;
10. Patients with known active hepatitis B or hepatitis C infection;
11. Patients who intend to use any other topical cream, lotion or preparation applied to the radiation treatment area;
12. Patients with known or suspected active drug or alcohol abuse;
13. Patients with any abnormal laboratory test value which, in the opinion of the investigator, would put the patient at risk by trial enrollment;
14. Participation in other interventional clinical studies within 30 days prior to consent;
15. Patients with known hypersensitivity to excipients in the drug product;
16. Patients receiving concomitant chemotherapy during the course of the planned radiation treatment regimen. Patients are eligible if they are receiving sequential, neoadjuvant or adjuvant chemotherapy that is not anticipated to be delivered during the time course of the radiation treatment regimen;
17. Patients unable to comply with the requirements of the study protocol or are unsuitable for the study for any reason in the opinion of the investigator;
18. Patients receiving any form of brachytherapy radiation treatment including a brachytherapy boost;
19. Patients receiving reverse-planned intensity modulated radiation treatment (IMRT).

Investigational product, dosage and mode of administration:

RTA 408 Lotion (0.5% and 3%) will be applied topically twice daily. On days of morning radiation treatments, the patient will apply the study drug at the radiation treatment center immediately after the radiation therapy concludes and at night before bed. On days of afternoon radiation treatments, the patient will apply the study drug in the morning at least 4 hours before radiation treatment and at night before bed. A thin layer of lotion will be applied to the irradiated area. RTA 408 Lotion or vehicle lotion should never be applied immediately before radiation treatment, and any residual lotion from a prior application should be removed prior to radiation treatment. If patients develop grade 2 or higher radiation dermatitis and the radiation dermatitis is believed to be inadequately controlled in the opinion of the Investigator, additional topical creams, lotions, hydrocortisone or other escape medications may be prescribed and then must be documented.

Duration of treatment:

RTA 408 Lotion will be administered topically to the radiation area twice daily: prior to initiation of radiation treatment (approximately 1 week), during radiation treatment (approximately 6 weeks), and after completion of radiation treatment (2 weeks). In cases where radiation treatment is delayed (e.g., delayed radiation treatment initiation or radiation treatment interruptions), the study drug application period may be extended from the expected 8-9 weeks up to a maximum of 13 weeks.

Reference therapy, dosage and mode of administration:

Vehicle lotion will be applied topically twice daily. On days of morning radiation treatments, the patient will apply the study drug at the radiation treatment center immediately after the radiation therapy concludes and at night before bed. On days of afternoon radiation treatments, the patient will apply the study drug in the morning at least 4 hours before radiation treatment and at night before bed. A thin layer of lotion will be applied to the irradiated area. RTA 408 Lotion or vehicle lotion should never be applied immediately before radiation treatment, and any residual lotion from a prior application should be removed prior to radiation treatment. If patients develop grade 2 or higher radiation dermatitis and the radiation dermatitis is believed to be inadequately controlled in the opinion of the Investigator, additional topical creams, lotions, hydrocortisone or other escape medications may be prescribed and then must be documented.

Criteria for evaluation:

[figure not shown]
Efficacy: Time-averaged change in dermatitis grade (CTCAE v4.03), Change in mean maximal dermatitis grade, percentage of patients with maximal dermatitis grade < 2, duration of CTCAE grade ≥ 2 .

Safety: Results of vital sign assessments, physical examinations, laboratory test results (clinical chemistry, hematology, urinalysis), concomitant medications, adverse events and serious adverse events

Pharmacokinetic variables: RTA 408 plasma concentration-time data

Statistical methods:

Sample size:

Statistical analysis: A statistical analysis plan (SAP) detailing the analyses described below will be developed prior to the database lock. The SAP will serve as the final arbiter of all statistical analyses. Data will be summarized overall using descriptive statistics. Continuous data will be summarized with number of patients (n), mean, median, minimum, maximum, standard deviation, coefficient of variation, and geometric mean (where applicable). Categorical data will be summarized using number of patients (n), mean, median, minimum, maximum, standard deviation, coefficient of variation, geometric mean (where applicable), frequency counts and percentages.

Primary efficacy analysis: For the primary efficacy analysis, a longitudinal mixed-model will be used to analyze the CTCAE dermatitis grades over time, incorporating the repeated measures design of the study. Treatment group and week of visit will constitute the main fixed effects of the model; study subject will represent the random effect; smoking status, breast cancer treatment prior to radiation therapy, and other covariates (such as cumulative radiation exposure) will be evaluated for inclusion in the model as covariates. A generalized mixed model will be used as the primary longitudinal model with additional sensitivity analyses performed as appropriate. A hierarchical approach will be used for analysis of the primary endpoint to control the type I error. RTA 408 treatment arms will be compared

with vehicle utilizing a hierarchical testing strategy to control the overall type I error. The primary efficacy analyses will first test the difference between RTA 408 Lotion pooled and vehicle lotion. If the first comparison is statistically significant, RTA 408 Lotion 3.0% will be compared to vehicle lotion. Otherwise, the second comparison will not be performed or the p-value will be considered nonsignificant. Similarly, only if the second comparison is statistically significant, RTA 408 lotion 0.5% will be compared to vehicle lotion.

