8. SELECTION AND WITHDRAWAL OF PATIENTS

8.1. Patient Inclusion Criteria

All patients must meet all of the following criteria to be included in the study:

1. Adult female patients (18 to 80 years of age, inclusive);
2. Patients diagnosed with ductal carcinoma in situ or non-inflammatory breast adenocarcinoma who have been referred for post-operative radiotherapy and have had no prior radiation treatment to that breast;
3. Patients planning to undergo 3D conformal radiation therapy to the whole breast (as part of breast-conservation therapy / lumpectomy) or chest wall (as part of post-mastectomy irradiation), with or without treatment of regional lymph nodes (i.e., axillary, supraclavicular, or internal mammary), using one of the following treatment schedules:
 - a. 45 – 50.4 Gy in 1.8 Gy per day, in addition to a mandatory 10-16 Gy boost
 - b. 46 – 50 Gy in 2 Gy per day, in addition to a mandatory 10-16 Gy boost;
4. Patients who received breast-conservation therapy / lumpectomy must be receiving $\geq 107\%$ of the total radiation dose (calculated from the total radiation dose including boost) to any portion of the breast, based on radiation inhomogeneity, **and/or** have a breast volume ≥ 1200 cc;
5. Female patients of childbearing potential who are willing to practice methods of birth control from screening through 1 month after applying the final dose of study drug;
6. Female patients of childbearing potential who are non-pregnant, non-lactating and have a negative pregnancy test result prior to enrollment in the study;
7. Patients willing and able to give written informed consent for study participation;
8. Patients willing and able to cooperate with all aspects of the protocol;
9. Patients for which at least 14 days have elapsed since breast conservation surgery, mastectomy surgery and/or chemotherapy prior to randomization;
10. Have adequate hematologic and organ function at screening as follows:
 - a. Hematologic: Absolute neutrophil count $\geq 1.5 \times 10^3$ / μ L, platelets $> 100 \times 10^9$ /L, hemoglobin ≥ 9 g/dL;
 - b. Hepatic: total bilirubin ≤ 1.5 times (X) upper limit of normal (ULN), ALT and AST \leq ULN;
 - c. Renal: serum creatinine ≤ 1.5 mg/dL

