8.3. Patient Re-screening

Reasons for study re-screening include the following:

- At the discretion of the investigator, a patient's planned radiation regimen is changed from a non-allowed regimen to a regimen listed in Section 8.1;
- Patients initially qualified for the study, but radiation treatment was delayed such that patients did not begin study drug for >45 days after Screening;
- Patients have experienced logistical/operational issues and the medical monitor has been notified;
- Patients have no changes in their radiation treatment plan and have undergone prior chemotherapy, but did not initially qualify for the study due to bone marrow toxicity associated with chemotherapy (absolute neutrophil count $\geq 1.5 \times 10^3 / \mu\text{L}$, platelets $> 100 \times 10^9 / \text{L}$, hemoglobin $\geq 9 \text{ g/dL}$);
- Patients had untreated bacterial, fungal, or viral skin infections and since have undergone treatment for this condition;
- Patients who may undergo re-screening with the approval of a medical monitor.

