8.4.1. Patient Discontinuation Criteria

Discontinuation refers to a patient stopping administration of study drug. Reasons for study drug discontinuation include the following:

- Occurrence of an adverse event (AE) or change in medical status that leads the investigator to be concerned about the patient's welfare
- Noncompliance with study procedures
- Pregnancy during the study
- Investigator unblinding of patient

Patients who are discontinued from study drug should still attend all study visits and undergo all study assessments, if possible.

The CTCAE version 4.03 will be used to define patient stopping criteria for systemic adverse events, except where related to transaminase laboratory values. The criteria for a stopping criteria for adverse events related to transaminase laboratory values will be defined using the FDA Guidance for Industry titled "Drug-Induced Liver Injury: Premarketing Clinical Evaluation" (July 2009) rather than CTCAE.

The determination stopping criteria will be defined in each patient as all toxicity \geq Grade 3 (using CTCAE, version 4.03), except as noted below:

- Grade \geq 3 skin toxicity, with the patient allowed to continue at the discretion of the investigator;
- Nausea and vomiting will be considered stopping criteria if Grade 3 toxicity persists after optimal medical therapy.

Any hepatobiliary disorders of \geq Grade 2 (from CTCAE, version 4.03, pages 24 – 25) will be considered adequate stopping criteria. Note that laboratory measurements are included in a separate section of the CTCAE.

Changes in ALT, AST, and total bilirubin levels must meet one of the following criteria to be considered a DLT:

- ALT or AST $>$ 8X ULN
- ALT or AST $>$ 5X ULN for more than 2 weeks
- ALT or AST $>$ 3X ULN and (total bilirubin $>$ 2X ULN or INR $>$ 1.5)
 - (Repeat testing every 72 to 96 hours until transaminase levels are below three times the ULN for at least one week or patient withdraws consent.)
- ALT or AST $>$ 3X ULN with the appearance of fatigue, nausea, vomiting, right upper quadrant pain or tenderness, fever, rash, and/or eosinophilia ($>5\%$)
 - (Repeat testing every 72 to 96 hours until transaminase levels are below three times the ULN for at least one week or patient withdraws consent.)

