## 1. INTRODUCTION

Study 408-C-1306 is a randomized, double blind, vehicle-controlled, parallel-group Phase 2 study designed to study the efficacy, tolerability and safety of two concentrations of RTA 408 Lotion (3% and 0.5%) versus vehicle in patients with breast cancer for whom radiation is recommended. This document describes the statistical analysis methods and data presentations that Reata Pharmaceuticals, Inc. (Reata) will use to analyze data from the study. [REDACTED],

[REDACTED] is the blinded study statistical group responsible for conducting the analyses described in this document. [REDACTED] will remain blinded to study treatment assignments until after the database is locked. Study related documents include the study protocol and case report form.

This version of the SAP describes the analyses planned prior to the database lock. Unless otherwise specified, the analyses described in this document will be performed after database lock for inclusion in the final clinical study report (CSR). Any substantive changes made to the statistical analysis plan after database lock will be clearly documented and a justification will be given in the CSR.

This SAP is based on Version 4 of the study protocol dated October 17, 2014. If the protocol is subsequently amended, this SAP may be amended as well. Should the SAP and the protocol be inconsistent with respect to the planned analyses, the language of the SAP is governing. All analyses will be conducted using SAS version 9.2 or higher.

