#### **4.4 Inclusion and Exclusion Criteria**

A listing will be provided for all randomized patients who did not meet all study entry criteria as defined by inclusion and exclusion criteria.

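### The synopsis and Section 8.1 give different bilirubin ceilings for the same entry criterion (2 × ULN against 1.5 × ULN); separately and minor, SAP 7.2.4 leaves two gaps in counting treatment-emergent laboratory abnormalities

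*Protocol*

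**What the plan says.** **Entry limits.** Inclusion criterion 10 appears twice in the protocol. In the synopsis the hepatic line reads "2 times (X) upper limit of normal (ULN), ALT and AST": total bilirubin may be up to 2 × ULN, and ALT and AST up to 2 × ULN. In Section 8.1, criterion 10b reads "1.5 times (X) upper limit of normal (ULN), ALT and AST": bilirubin may be up to 1.5 × ULN, and ALT and AST up to ULN, printed with no multiplier.

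**Which list applies.** Section 8.1 opens with "All patients must meet all of the following criteria to be included in the study", and the re-screening text in Section 8.3 refers "to a regimen listed in Section 8.1". The synopsis presents its list as key criteria only. The SAP has a precedence clause in its Introduction: "Should the SAP and the protocol be inconsistent with respect to the planned analyses, the language of the SAP is governing". That clause concerns analyses, not eligibility.

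**Use of the criteria.** SAP 4.4 states: "A listing will be provided for all randomized patients who did not meet all study entry criteria as defined by inclusion and exclusion criteria". It does not say which hepatic limits define a failure.

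**Laboratory abnormalities.** SAP 7.2.4 counts three things as treatment-emergent: a move from normal to abnormal, up to the last dosing date; a reversal from low to high or high to low; and any abnormality where baseline is missing. SAP 7.1.3.1 lets treatment-emergent adverse events start up to 30 days after the last dose.

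**The concern.** An eligibility threshold should have one value. Up to 35 centers screen against this protocol, and a site working from the synopsis would accept a bilirubin result that Section 8.1 rejects. The same patient would be a valid enrolment on one reading. On the other she would be a protocol deviation and an entry in the SAP 4.4 listing. Safety is one of the two primary objectives, and protocol Section 5.1 names the liver as a target organ in the 13-week rat dermal study, so the hepatic line should not be left ambiguous.

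The SAP 7.2.4 matter is separate and smaller. An already abnormal value that gets worse in the same direction is not counted in that table. Nor is a first abnormality at the follow-up visit in a patient who was normal at baseline, although an adverse event starting then can be.

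**Working it through.** No sample-size or error-rate calculation applies. The check compares the texts and uses simple ratios.

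**1. Criterion 10, side by side**

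| Item | Synopsis | Section 8.1 | Agree? |
|---|---|---|---|
| Neutrophils | ≥ 1.5 × 10³/µL | ≥ 1.5 × 10³/µL | yes |
| Platelets | > 100 × 10⁹/L | > 100 × 10⁹/L | yes |
| Hemoglobin | ≥ 9 g/dL | ≥ 9 g/dL | yes |
| Total bilirubin | ≤ 2 × ULN | ≤ 1.5 × ULN | **no** |
| ALT, AST | ≤ 2 × ULN | ≤ ULN as printed | **to be confirmed** |
| Creatinine | ≤ 1.5 mg/dL | ≤ 1.5 mg/dL | yes |

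Only the hepatic line differs. Neither list is an amendment log.

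**2. Bilirubin.** Ratio of ceilings: 2/1.5 = 1.33. The lists disagree for values above 1.5 and up to 2.0 × ULN, a band of 2.0 − 1.5 = 0.5 × ULN. The documents give no distribution of screening bilirubin, so the number of patients in that band cannot be estimated.

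**3. ALT/AST.** The result depends on the multiplier that Section 8.1 was meant to carry:
- none (as printed): 2/1 = 2.0
- 1.5: 2/1.5 = 1.33
- 2: 2/2 = 1.0, that is, no conflict

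**4. What depends on the limits.** The ITT population is everyone randomized (SAP 3.2.1). The safety population is everyone who received a dose (SAP 3.2.2). No per-protocol set is defined. The limits therefore bear on enrolment, on deviations (protocol 16.6, SAP 4.7) and on the SAP 4.4 listing.

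**5. Distance to the combined liver criterion.** One criterion in protocol 8.4.1 contains the wording "3X ULN and (total bilirubin". It needs ALT or AST above 3 × ULN together with either bilirubin above 2 × ULN or INR above 1.5. Margin on the bilirubin limb at entry: 2.0 − 2.0 = 0 under the synopsis and 2.0 − 1.5 = 0.5 × ULN under Section 8.1. Margin on the ALT/AST limb, even under the synopsis: 3 − 2 = 1 × ULN.

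**6. SAP 7.2.4, same-direction change.** Section 8.1 itself allows entry with bilirubin between 1 and 1.5 × ULN, or with low hemoglobin down to 9 g/dL. High to higher, or low to lower, meets none of the three rules. If the synopsis limits applied, ALT entering at 2 × ULN and rising to 6 × ULN would also go uncounted. SAP 7.2.5 does not close this gap, because its categories are only Normal, Low and High.

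**7. SAP 7.2.4, cutoff.** Table 3 schedules chemistry, hematology and urinalysis at Visit 12, about 4 weeks after the last dose. With the 2-day allowance this is 28 − 2 = 26 to 28 + 2 = 30 days. That is after the last dosing date, so the normal-to-abnormal rule excludes it, yet it lies within the 30-day adverse event window.

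**The case against.** The case for doing little is strong in several places.

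- **Section 8.1 is evidently the operative list and is the stricter one.** Anyone who meets it also meets the synopsis, and protocol 9.8.2 repeats that all criteria must be met. Harm needs a site that screens from the synopsis alone. Exclusion criterion 13, in both lists, also lets the investigator exclude any patient whose laboratory value puts her at risk. This stands and lowers the weight. It does not remove the conflict: calling the synopsis list key criteria explains omissions, not a different number for the same criterion.
- **No analysis changes.** This stands. The matter is an internal inconsistency, not an analysis choice.
- **A reader might infer a certain twofold ALT/AST conflict.** The documents do not support that. A multiplier may have been lost in typing or in reading the PDF.
- **A reader might infer that a patient admitted under the synopsis has no margin before stopping drug.** She does not. Zero margin applies to one limb of a joint criterion, and ALT or AST must still rise above 3 × ULN.
- **A reader might infer that SAP 7.2.4 hides a liver signal.** It does not. By-visit change, change to worst value where appropriate, listings and adverse event tables can still show these values, and Phase 1 plasma concentrations were near or below the quantitation limit. Confining emergent flags to time on drug is also a defensible convention.
- **A reader might infer that the three SAP 7.2.4 rules have different windows.** That rests on silence. The reversal rule directly follows the dated one and may share its cutoff; the wording is ambiguous at most.

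**Conclusion.** The bilirubin conflict is certain: 2 × ULN in one place and 1.5 × ULN in another, both current, with no clause that settles eligibility. Its size is a ratio of 1.33 and a disputed band of 0.5 × ULN; the number of patients affected is unknown. It bears on enrolment, deviation recording and one listing. It does not alter an analysis population or the primary efficacy analysis.

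The ALT/AST difference is a query for the sponsor, with a ratio anywhere from 1.0 to 2.0 depending on the intended multiplier.

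The SAP 7.2.4 gaps are real as written but minor. They affect counts in the treatment-emergent laboratory summaries only, and the under-count cannot be computed from the documents. The Visit 12 timing assumes that dosing was completed and that the visit fell within 2 days of schedule.

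Overall this is minor to a low-priority should-fix, and that grade rests on the bilirubin conflict alone.

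**What to change.** **Protocol.** Confirm the intended hepatic limits and state one set in both the synopsis and Section 8.1. The default is the stricter bilirubin limit of 1.5 × ULN, with the ALT/AST multiplier confirmed against the source. State in SAP 4.4 that the listing uses that set.

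**SAP 7.2.4.** (a) Count worsening in the same direction by at least one CTCAE v4.03 grade from baseline, for tests that have a grade. (b) State one window for all three rules, at least 30 days after the last dose to match adverse events. Later results from patients who stopped drug early but kept attending can be shown separately.

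**Optional.** Section 8.4.1 says "CTCAE version 4.03 will be used to define patient stopping criteria for systemic adverse events, except where related to transaminase laboratory values", so a by-arm table of patients reaching its ALT, AST and bilirubin multiples would complement the graded counts. INR is in neither document's laboratory panel, so that limb could be filled only where a value happens to exist.

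**Cost.** One protocol clarification, a sentence in SAP 4.4 and two wording changes in SAP 7.2.4, with no new data collection. The downside is slightly higher counts of treatment-emergent abnormalities, some of them minor or arising off drug.
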